3.1.2 Optional Open-label Extension

Subjects who either complete the Randomization Period of the study (up through the Test of Cure Visit), or who are prematurely discontinued from study treatment during the Randomization Period due to worsening of signs and/or symptoms of otomycosis in the judgment of the investigator, will be offered the opportunity to participate in an optional open-label extension, if they have a visual presence of fungal elements in at least one ear treated during the Randomization Period. Only the ear(s) that were treated in the Randomization Period will be potentially eligible for treatment during the Optional Open-label Extension.

All subjects in the Optional Open-label Extension will receive miconazole oil for 14 days. No unblinding of the subject's treatment in the Randomization Period will occur at this time.

Before a subject enters the Optional Open-label Extension, all procedures for the Test of Cure Visit will be completed for that subject; however, a fungal culture will not be required at this visit for subjects known to have a negative fungal culture at Screening/Baseline, as assessed after at least 14 days of incubation by the clinical laboratory performing the fungal culture.

At the first visit of the Optional Open-label Extension (Day OLE1, which will occur while the subject is already onsite for the Test of Cure or Early Termination Visit from the Randomization Period), study drug (miconazole oil) will be weighed and dispensed to the subject along with a subject diary. Subjects or their caregivers will administer the first dose of miconazole oil at the site. AEs and concomitant medications will then be assessed. Subjects will then continue to administer miconazole oil and to complete the subject diary twice per day for a total of 14 days, following the same instructions as provided at the Screening/Baseline Visit on Day 1.

Subjects will return to the clinic on Day OLE15 for the End of Treatment Visit, at which time a clinical evaluation of the signs and symptoms of otomycosis will be performed, as well as an assessment of AEs and concomitant medications. A urine pregnancy test will be performed in women of childbearing potential. The subject will return all unused miconazole oil along with the completed subject diary.

The purpose of the Optional Open-label Extension is safety and to provide supportive evidence of efficacy. Efficacy assessments will include assessments of clinical signs and symptoms of otomycosis. Safety assessments will include AEs.

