1.2 Study Purpose

The purpose of this study is to gather confirmatory data on the efficacy and safety of 2% miconazole oil after topical otic administration in subjects with otomycosis. During the Randomization Period of the Enrollment A portion of the study, a 14-day regimen of twice-daily administration of 2% miconazole oil will be compared with the same treatment regimen using the product vehicle. During the Optional Open-label Extension of the Enrollment A portion and the Enrollment B portion of the study, a 14-day regimen of twice-daily administration of 2% miconazole oil will be administered in an open-label fashion in order to gather safety information in additional subjects.

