2 STUDY OBJECTIVES

[figure not shown]
The objectives of the study are to:

- Confirm the efficacy of miconazole oil compared with vehicle over a 14-day treatment duration in subjects with otomycosis
- Assess the safety of miconazole oil over a 14-day treatment duration

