3.1 Enrollment A

The study will start with Enrollment A, in which an estimated 220 male or female subjects with otomycosis will receive study drug, although this number may be higher or lower depending on the percentage of subjects eligible to be included in the modified intent-to-treat (MITT) population (see Section 10.4.2). Subjects will be randomly assigned in a 1:1 ratio to receive miconazole oil or vehicle, for 14 days. The study drug will be administered as 5 drops per ear at ~30 mg per drop instilled into the external ear canal of the ear(s) affected by otomycosis.

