10.5 Statistical Methods

10.5.1 Efficacy Analyses

The primary population for efficacy analyses will be the MITT population (see Section 10.4). Efficacy analyses will also be performed on the ITT and the PP populations and will be considered supportive.

The primary analysis will be conducted once Enrollment A is complete.

The number and percent of subjects who demonstrate a positive outcome for the primary efficacy outcome as well as all secondary and tertiary efficacy outcomes will be presented.

The primary endpoint, defined as the percentage of subjects at the Test of Cure Visit with “therapeutic cure”, will be compared between groups using a chi-square test with a 2-sided significance level of 0.05.

The secondary endpoints will be analyzed analogously to the primary endpoint.

In Enrollment A in cases of bilateral otomycosis, if only 1 ear has a positive fungal culture at Screening/Baseline, that ear will be used as the study ear for efficacy analyses. If both ears have a positive fungal culture at Screening/Baseline, the ear with the worse infection at Screening/Baseline, as assessed by the investigator by taking into account clinical signs and symptoms, will be used as the study ear for efficacy analyses. If both ears have a positive fungal culture at Screening/Baseline and are determined by the investigator to have the same degree of infection at Screening/Baseline, the left ear will be used as the study ear for the purposes of efficacy analyses.

Descriptive statistics will be provided for otomycosis signs and symptoms and also for clinical cure, modified therapeutic cure, and therapeutic improvement; each at Day 15 will be summarized using the ITT population for both the Randomization Period and the Optional Open-label Extension.

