10.5.2 Safety Analyses

Safety summaries will be conducted using two safety populations (see Section 10.4.4). All AEs occurring during the study will be recorded and classified using terminology from the Medical Dictionary for Regulatory Activities (MedDRA). All reported treatment-emergent adverse events (TEAEs), defined as any AE with an onset on or after the date of first study drug application, will be summarized. Summaries will provide the number of subjects reporting TEAEs, system organ class, preferred term, severity, and relationship to study drug. When summarizing TEAEs by severity or relationship to study drug, each subject will be counted only once within a system organ class or a preferred term using the event with the greatest severity or causality, respectively, within each category. All reported SAEs will be summarized by the number of subjects reporting the event, system organ class, preferred term, severity, and relationship to study drug.

Summaries will be provided separately for the blinded and unblinded portions. Specifically, summaries will be provided by treatment group for the Randomization Period using the Randomization Period safety population, and for all open-label subjects using the Open Label safety population.

All information pertaining to AEs noted during the study will be listed by study portion (Enrollment A or Enrollment B), study period (Randomization or Optional Open-label), as applicable, treatment group, and subject and will include a verbatim description of the event as reported by the investigator, as well as the preferred term, system organ class, start date, stop date (if stopped), seriousness, severity, action taken regarding the study drug, corrective treatment, outcome, and relationship to the study drug. In addition, a listing of subjects who prematurely discontinue from the study due to AEs will be provided as well as a listing of subjects who report an SAE.

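### The open-label safety summary pools first-course (ex-vehicle) and second-course (ex-miconazole) extension subjects, so it does not isolate the 14-day course; extension results should also be shown by randomized arm

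*Combined protocol and SAP*

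**What the plan says.** Section 3.1.2 offers the extension to subjects who complete the Randomization Period, or who stop study treatment early because their otomycosis worsens, "if they have a visual presence of fungal elements in at least one ear treated during the Randomization Period". The randomized arm plays no part in entry, and no one is unblinded at that point. Then: "All subjects in the Optional Open-label Extension will receive miconazole oil for 14 days".

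The stated aims are in section 2, "Assess the safety of miconazole oil over a 14-day treatment duration", and in section 3.1.2, "The purpose of the Optional Open-label Extension is safety and to provide supportive evidence of efficacy".

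For safety, section 10.4.4 combines the extension with Enrollment B. Section 10.5.2 gives summaries by treatment group for the Randomization Period, "and for all open-label subjects using the Open Label safety population". For efficacy, section 10.5.1 names the descriptive outcomes (therapeutic improvement, modified therapeutic cure, clinical cure, and the signs and symptoms themselves) and then says: "each at Day 15 will be summarized using the ITT population for both the Randomization Period and the Optional Open-label Extension". That sentence does not mention arm.

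**The concern.** The two kinds of extension subject answer different questions. Ex-vehicle entrants start miconazole oil for the first time. Ex-miconazole entrants repeat it, and they are selected for still having visible fungal elements after active treatment.

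Elsewhere the protocol keeps these exposures apart. The exposure count in section 3.4.2 draws only ex-vehicle subjects from the extension. Enrollment B exclusion 9 (section 4.2.2) bars former Enrollment A participants unless it is known that they were never given miconazole oil, and exclusion 8 bars the 14-day miconazole group of the Phase 2 study. Enrollment B is thus kept free of people who had a 14-day course in this program, and its data are then pooled with extension subjects who may have had one.

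At stake is the open-label adverse-event table. Its percentage mixes first-course and repeat-course experience, and a reader cannot tell whether repeat use pushed it up or down. Exposure beyond 14 days will exist in the data, but no planned summary shows it.

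**Working it through.** **1. The plan's exposure count (section 3.4.2).** Inputs: 110 per arm, 90% completing 14 days, 50% of vehicle subjects entering the extension, 170 in Enrollment B.
- Randomized miconazole: 110 × 0.90 = 99 (plan: about 100)
- Ex-vehicle in the extension: 110 × 0.50 = 55; 55 × 0.90 = 49.5 (plan: about 50)
- Enrollment B: 170 × 0.90 = 153 (plan: about 150)
- Total: 99 + 49.5 + 153 = 301.5, against the target of 300

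The target reproduces with no second-course subjects in it.

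**2. Cumulative product per ear.** Inputs: "5 drops per ear at ~30 mg per drop" (section 3.1) and "a 14-day regimen of twice-daily administration of 2% miconazole oil" (section 1.2).
- One course: 14 × 2 × 5 × 30 mg = 4,200 mg = 4.2 g
- Two full courses: 8.4 g, a ratio of 2.0
- After an early stop on day d, the ratio is (d + 14)/14. For assumed stops after 3, 7 and 10 days it is 1.2, 1.5 and 1.7.

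The doubling refers to miconazole oil. Ex-vehicle subjects have also had a prior course of the oil base, so first course here means first active course.

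**3. How many second-course subjects.** The plan gives no figure. Assume that 10% to 50% of the 110 randomized to miconazole enter, with 55 ex-vehicle entrants and 170 in Enrollment B.

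| Ex-miconazole entrants (assumed) | Share of extension | Share of Open Label safety population |
|---|---|---|
| 11 (10%) | 11/66 = 17% | 11/236 = 4.7% |
| 44 (40%) | 44/99 = 44% | 44/269 = 16.4% |
| 55 (50%) | 55/110 = 50% | 55/280 = 19.6% |

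The middle row is close to what follows if the same fraction of uncured subjects enters from each arm. Section 10.3 implies 75% uncured on miconazole and 92.9% on vehicle. Then 0.50/0.929 = 54% of the uncured enter, and 110 × 0.75 × 0.54 is about 44. This treats absence of therapeutic cure as a proxy for visible fungal elements, which the documents do not establish.

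**4. Effect on the table as planned.** Let p be the rate in the 225 first-course subjects (55 + 170), q the rate in m second-course subjects. The pooled rate is (225p + mq)/(225 + m). Assume q between 0.5p and 2p, and m = 55.
- p = 10%: from (22.5 + 2.75)/280 = 9.0% to (22.5 + 11)/280 = 12.0%
- p = 27.3% (6/22, the Phase 2 row for general disorders and administration site conditions in Table 1): from 24.6% to 32.7%

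The multipliers are assumptions. The documents give no adverse-event rate for a second course, so even the direction is open.

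**5. Primary analysis.** It uses Randomization Period data only. Recomputed power at 64 per group for 25.0% against 7.1% is 79.5%, against the stated 80%, and does not depend on the extension.

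**The case against.** The main questions are answered elsewhere. Efficacy rests on the randomized Test of Cure comparison, and the extension is only supportive. Safety of a 14-day course is tabulated by arm for the Randomization Period, and Enrollment B adds to it. This stands, and it limits the point to descriptive reporting.

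The efficacy gap may be one of wording. The synopsis (Statistical Analyses) promises descriptive results by treatment group at each evaluation, which could be read to cover Day OLE15. The adverse-event listings carry study period and treatment group, and section 10 leaves full detail to a separate statistical analysis plan that is not in the text reviewed. So for efficacy only ambiguity in the protocol can be claimed. For safety the objection is weaker: combining is a stated rule, a listing is not a summary, and the text does not say whether treatment group in the extension means the original arm.

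Four stronger readings are tempting and not supported:
- That the extension cannot support the 14-day question. It can: the ex-vehicle subjects supply first-course data, and only the planned tables fail to separate them.
- That ex-vehicle entrants replicate the randomized course. Table 3 schedules no ear cleaning, Day 8 visit, fungal culture or Test of Cure Visit in the extension, and entrants are selected for visible fungal elements.
- That ex-miconazole entrants are people who tolerated a first course. Section 3.1.2 admits subjects who stopped for worsening, and section 5.1.2 foresees entrants who used a topical corticosteroid for an adverse event after stopping.
- That pooling lowers a therapeutic cure rate by a calculable amount. Therapeutic cure needs a culture, and none is taken in the extension.

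**Conclusion.** The point holds as a reporting gap of modest size. The protocol pools first-course and second-course miconazole subjects with Enrollment B in one open-label safety summary, so that percentage does not isolate the 14-day course named in the objective, and repeat-course exposure of up to 28 days is not summarized. For extension efficacy, a split by arm is not clearly stated.

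On the assumptions shown, second-course subjects are 4.7% to 19.6% of the pooled safety population. At the upper end of entry, a 10% adverse-event rate could read as 9.0% to 12.0%. These sizes rest on assumed entry and on an assumed relation between first-course and second-course rates. The twofold exposure is a maximum. No hypothesis test, sample size or exposure target changes.

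**What to change.** Amend sections 10.5.1 and 10.5.2 so that extension adverse-event summaries and sign and symptom summaries are shown by randomized arm (ex-vehicle, first active course; ex-miconazole, second active course) as well as in total. Label the second-course column as cumulative exposure of up to 28 days. Rely on first-course subjects for open-label statements about the 14-day regimen. State that treatment group in the extension listings means the original randomized arm. If the separate statistical analysis plan already does this, confirm it and align the protocol text.

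The assignment is available after the Enrollment A unblinding described in section 3.1.3, so no new data are needed. The cost is two extra columns with smaller denominators: about 55 entrants in the ex-vehicle column and an unknown, possibly small, number in the other.

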3.1.3 Timing of Analysis for Enrollment A

Data for Enrollment A will be unblinded after all subjects planned for Enrollment A have completed both the Randomization Period and the Optional Open-label Extension, so that analyses from Enrollment A can be conducted even if Enrollment B is still ongoing (i.e., before the conclusion of Enrollment B).

3.2 Enrollment B

Enrollment B may be initiated while Enrollment A is still actively enrolling subjects. An estimated 170 male or female subjects will receive study drug (miconazole oil) in Enrollment B, although this number may be higher or lower depending on the total number of subjects needed to achieve at least 300 subjects who are exposed to miconazole oil for 14 days in the study overall who are evaluable for safety.

At Screening/Baseline (Day B1), potentially eligible subjects will provide informed consent, and subjects will undergo screening evaluations to include a physical examination and an evaluation of medical history. Urine will be obtained for pregnancy screening in female subjects of childbearing potential. Prior and concomitant medications will be reported. Subjects who meet all eligibility criteria will be entered into the study. Study drug will be weighed and dispensed to the subject along with a subject diary. The subject will then begin treatment with miconazole oil. In subjects who do not have otomycosis, treatment will be in the left ear if both ears are otherwise eligible; if only one ear is eligible, treatment will be in that ear. In subjects who have otomycosis (i.e., any signs and/or symptoms consistent with a clinical diagnosis of otomycosis in the judgment of the investigator), treatment will preferably be in the ear(s) with otomycosis, provided the ear(s) meet all eligibility criteria. If both ears are judged by the investigator to have otomycosis and both meet all eligibility criteria, both ears may be treated. The subject or caregiver will instill the first dose of miconazole oil at the site, under the supervision of the investigator or site personnel. AEs will then be assessed. The subject will then leave the clinic and continue to administer miconazole oil and to complete the subject diary twice per day, following the same instructions for miconazole oil administration as in Enrollment A.

Subjects will return to the clinic on Day B15 for the End of Treatment Visit, at which time AEs and concomitant medications will be assessed. Subjects will return all unused miconazole oil along with the completed subject diary. A urine pregnancy test will be performed in women of childbearing potential.

Safety assessments will include AEs.

3.3 Timing of Subject Recruitment Into Enrollment A and Enrollment B

The study will start with Enrollment A, which will continue until the sponsor determines that a sufficient number of subjects (see Section 3.4) has been recruited to conduct the planned

analyses for Enrollment A, at which time the sponsor (or designee) will notify all study sites to terminate further enrollment into the Enrollment A portion of the study.

Recruitment of subjects into Enrollment B will begin when the sponsor (or designee) notifies sites to begin recruiting subjects into Enrollment B, and will end when the sponsor (or designee) notifies study sites to pause or permanently terminate recruitment of subjects into Enrollment B. Enrollment B may occur over one or multiple time periods, each of which will begin and then pause (or permanently end) upon sponsor (or designee) notification to the study sites. The purpose of this mechanism is to allow concurrent enrollment of Enrollment A and Enrollment B at times (such as during the wintertime) when recruitment into Enrollment A is likely to be diminished due to a lower expected incidence of otomycosis, while also allowing the sponsor the flexibility to pause or permanently terminate recruitment into Enrollment B for reasons including (but not limited to) time periods during which a higher incidence of otomycosis is expected (at which times the sponsor may wish for the focus of the study to be on recruitment of subjects into Enrollment A), or evaluation by the sponsor of the number of subjects still needed for Enrollment B (see Section 3.4).

At times when Enrollment A and Enrollment B are concurrently ongoing, if a subject is found to be eligible for both Enrollment A and Enrollment B, the subject should be enrolled into Enrollment A whenever possible.

3.4 Number of Subjects

Approximately 390 total subjects are estimated to be enrolled into the study (~220 subjects estimated for Enrollment A and ~170 subjects estimated for Enrollment B) as described in Section 3.4.1 for Enrollment A and in Section 3.4.2 for Enrollment B.

3.4.1 Enrollment A

An estimated 220 eligible subjects are planned to be enrolled in Enrollment A in order to achieve at least 128 evaluable subjects (i.e., included in the MITT population, defined as those who were randomized with a positive fungal culture at Screening/Baseline). The number of subjects who are enrolled may be higher or lower than 220 depending on the percentage of subjects eligible to be included in the MITT population; enrollment in Enrollment A will continue until the required numbers of subjects have been achieved.

3.4.2 Enrollment B

An estimated 170 eligible subjects are planned to be enrolled in order to achieve at least 300 total subjects in the study (including both Enrollment A and Enrollment B) who are exposed to miconazole oil for 14 days who are evaluable for safety. This number has been estimated on the basis of the following assumptions:

- A total of 220 subjects will be enrolled into the Randomization Period of Enrollment A, with 110 subjects exposed to active treatment with miconazole oil (on the basis of the 1:1 randomization for the Randomization Period), and 110 subjects exposed to the vehicle treatment:

- Of the 110 subjects exposed to active treatment (miconazole oil) in the Randomization Period, ~90% (100 subjects) will complete the full 14 days of treatment, with the remaining ~10% (10 subjects) completing less than the 14-day treatment course
- Of the 110 subjects exposed to vehicle treatment in the Randomization Period, ~50% (55 subjects) will opt to participate in the Optional Open-label Extension of Enrollment A, with the other ~50% (55 subjects) concluding participation in the study
- Of the 55 subjects exposed to miconazole oil treatment in the Optional Open-label Extension, ~90% (50 subjects) will complete the full 14 days of treatment, with the remaining ~10% (5 subjects) completing less than the 14-day treatment course
- On the basis of these assumptions, ~150 subjects will have been exposed to miconazole oil for the full 14-day treatment during Enrollment A (100 subjects during the Randomization Period and 50 subjects during the Optional Open-label Extension), and an additional ~150 subjects exposed to miconazole oil for the full 14-day treatment will be needed to achieve the ≥ 300 total subjects required to be exposed to miconazole oil for the full 14-day treatment
- Assuming ~90% of subjects enrolled into Enrollment B complete the full 14 days of open-label treatment with miconazole oil, ~170 subjects will be required to be enrolled in Enrollment B in order to achieve ~150 subjects who complete the full 14-day treatment with miconazole oil
- Therefore, ~150 subjects from Enrollment A and ~150 subjects from Enrollment B are estimated to be needed for at least 300 total subjects in the study who are exposed to miconazole oil for a full 14 days.

The actual number of subjects enrolled into Enrollment B may therefore be higher or lower than 170 depending on the accuracy of the assumptions as stated above, including the number of subjects who have completed a full 14 days of treatment with miconazole oil in Enrollment A as well as in Enrollment B. Enrollment will continue into Enrollment B until the required number of subjects exposed to miconazole oil for 14 days and evaluable for safety has been achieved.

